3. PROTECTION OF HUMAN SUBJECTS

1. Risks to Human Subjects:

1.a. Human Subjects Involvement, Characteristics, and Design: 80% of older adults develop delirium during their ICU stay. Presence of delirium predisposes older adults to immediate in-hospital complications including a longer length of ICU and hospital stay, increased risk of in-patient mortality and elevated costs of care. In addition, ICU delirium is associated with long-term post-discharge complications such as development of cognitive impairment and dementia. Our team is proposing to conduct a randomized clinical trial called "Decreasing Delirium through Music (DDM) in Critically III Older Adults" to evaluate the efficacy of a sevenday slow-tempo music intervention on the primary outcome of delirium/coma free days among mechanically-ventilated older adults admitted to the ICU.

The target population will be English-speaking; mechanically ventilated adults aged 50 and older who have been admitted to the intensive care unit in either Eskenazi Health or Methodist Hospital in Indianapolis or the Mayo Clinic in Rochester. The intervention comprises slow-tempo relaxing music versus a silence track attention control delivered twice daily for seven days. The primary outcomes will be delirium/coma free days. The enrolled population will also include women and minorities who meet the inclusion criteria. Subjects will be excluded as follows: [1] History of dementing illnesses and other neurodegenerative diseases such as Alzheimer's disease or vascular dementia; [2] Psychiatric illness which is not well controlled [3] Alcohol withdrawal symptoms/concern for withdrawal; [4] Suspected or confirmed drug intoxication/overdose, [5] Traumatic brain injury, ischemic or hemorrhagic cerebrovascular accident, or undergoing neurosurgery; [6] Uncorrected hearing or vision impairment including legal blindness; [7] Incarcerated at the time of study enrollment, [8] Enrolled in another clinical trial which does not permit co-enrollment

After obtaining approval from the local institutional Review Board (IRB) and the ICU leadership at each hospital, subjects or their legally authorized representative will be approached for participation into the study. After enrollment the subjects will be randomized into two groups, slow-tempo music intervention and silence track attention control. The interventionist research staff will initiate the study intervention. The research staff will perform blinded outcomes assessment including delirium/coma free days, delirium severity, pain, and anxiety during the ICU stay. After discharge, at 3 months, research assistants will perform cognition assessment, and will collect depression and anxiety measures over the phone.

1.b. Sources of Materials: During the hospital stay, research assistants will review the medical records and conduct delirium, coma, pain, and anxiety assessments. The blinded research assistants will also be collecting information on physiologic status (blood pressure, height, weight, heart rate, respiratory rate). The assessors will also conduct a medical record review to assess subject's chronic conditions (Charlson comorbidity index) and severity of medical illness (APACHE II index, SOFA). Study specific blood specimens will provide biomarker data.

All data gathering is done initially with subjects or their legally authorized representatives in the ICU and afterwards at the 3 months post hospital discharge follow-up. Data will be linked to participants through the use of a unique identifying number. Only persons on the research team will have access to the data. All data are collected for research purposes only. Case Report Forms (CRFs) will be stored in locked filing cabinets at Regenstrief Institute or Mayo Clinic and all data will be entered into electronic case report forms (eCRFs) in a secured password-protected database. All study data will be entered via a password-protected, study specific REDCap (Research Electronic Data Capture) database website. REDCap was developed specifically around HIPAA- Security guidelines and has been disseminated for use locally at other institutions and currently supports > 140 academic/non-profit consortium partners and 11,000 research end-users (www.project-redcap.org).

1.c. Potential Risks:

- (1) Fatigue, anxiety, stress, or embarrassment from the assessments. Emotional distress may result from answering health and behavior questions. Testing may also create anxiety, stress, or embarrassment at perceived performance. Participants may also become fatigued during the testing.
- (2) Exposure of confidential information. There is the potential for loss of privacy or confidentiality due to the data collection efforts of this study.

- (3) Discomfort with music delivery. There is potential for discomfort, infection, and irritation with use of the headphones. Another potential risk is that a subject could have an adverse emotional response to a certain piece of music. The potential risk for an adverse emotional response to music is thought to be low in regards to the music planned for our study playlist. Our music therapist consultant has extensive professional experience with ICU patients receiving mechanical ventilation. Depression and suicidal ideation. The duration of the study intervention is limited to the ICU: therefore adverse events related to the intervention occurring after the date of discharge are unlikely. Because research staff will continue to collect data from participants for 3 months after discharge, and because psychological complications have been described in ICU survivors, study staff will recognize worrisome conditions such as suicidal ideation or other emergent concerns of clinical conditions (chest pain, etc) during any study interaction. Study personnel will follow a scripted protocol to notify the appropriate medical personnel and the PI so that appropriate notification and clinical follow-up is ensured. The PI or delegated study personnel will notify the appropriate provider or emergency personnel depending on the severity of the presentation. Even in depression trials conducted by Regenstrief investigators with clinically depressed patients, this is only an occasional event, and in the present study we expect it to be rare. Nonetheless, we will train study personnel in the recognition and communication of such events to ensure prompt response to emergent reports if they occur. Risks related to blood sample collection will be minimized by use of clinical nurses for sample collection, use of existing intravascular devices for drawing blood whenever possible, and transport of the samples using lab best practices, and labelling the samples with deidentified labels.
- (4) Subjects may have pain, bruising or very rarely get an infection from the blood draw. To minimize these problems, blood will be drawn by trained staff using sterile procedures.

2. Adequacy of Protection Against Risks:

2.a. Recruitment and Informed Consent: Eligible subjects will be identified through the intensive care units census to which they are admitted. A waiver of consent documentation will be obtained for recruitment purposes only. Study personnel will consent the patient or their legally authorized representative (if the patient is unable to consent for themselves).

2.b. Protections Against Risk:

- (1) Fatigue, anxiety, stress, or embarrassment from the training or testing sessions. All questions planned for this study are part of validated standardized instruments, and we are not asking any questions that do not directly relate to the study purpose. Research staff will be trained in their proper use and in the importance of privacy and sensitivity to the participant's time. They will be trained to be alert and sensitive to signs of fatigue and other symptoms and to take appropriate actions when they are present.
- (2) Exposure of confidential information. Indiana University requires certification of training in protection of human subjects in research. The investigators, interventionist, assessors, and all key personnel have or will have successfully completed training and certification in these courses. All research involving the use of these data must be reviewed and approved by the IRB. We will assure the privacy of subjects and confidentiality of study data by assigning unique identifiers to track participants' data (rather than using names or hospital or social security numbers) and keep all records under lock with access only by study personnel. These procedures have been dutifully adhered to in prior studies. The final data files for this study will be merged, maintained, and analyzed on servers managed by the Division of Biostatistics, Department of Medicine, Indiana University School of Medicine. We will also utilize these rigorous protocols to protect confidentiality of biomarker analyses which include genetics and epigenetics associations. Our group has extensive experience in the handling and security of PHI. None of the individual participant data will be identifiable in published reports or manuscripts and the analyzable datasets will not contain the participant's unique identifier.
- (3) Discomfort with music delivery. Patients will be monitored for adverse events on a daily basis. Adverse events will be reported to the Institutional Review Board (IRB), data safety officer, and PIs immediately. In our prior work, we have not experienced any adverse events related to the study protocols. All infection control guidelines will be followed based on each hospital's policy. Patient risks will be minimized through the use of quality electronic devices, their regular cleaning and maintenance. If patients endorse discomfort from headphones, they will be switched to another set. In case of an adverse emotional response to music, subjects will be informed that they are free to withdraw from the study at any time they so desire without affecting their care. In previous work by the PI in which subjects listened to music from a discrete collection, no adverse emotional responses to music has occurred, thus we believe our plan here will be equally effective.
- (4) Depression and suicidal ideation: During follow-up assessments it is possible that participants endorse

suicidal ideation on the PHQ-9. We have handled them extensively in our prior m-CCRP and IMPROVE trials and have developed a suicide response protocol. A positive PHQ-9 will be followed by the Columbia Suicide Severity Rating Scale (C-SSRS) questions. If a participant answers yes to any C-SSRS question, the PI ([name]) will be notified immediately who will contact the family member to arrange transfer to the ER. If the participant does not answer yes to any C-SSRS question, the RA will still notify [name] who will contact the PCP of the patient and will arrange for an urgent follow-up.

- (5) Subjects may have pain, bruising or very rarely get an infection from the blood draw. To minimize these problems, blood will be drawn by trained staff using sterile procedures. Existing intravascular devices for drawing blood will be used whenever possible.
- **3. Potential Benefits of Proposed Research to Human Subjects and Others:** Participants may experience short-term benefits such as improve delirium/coma free days, lower delirium severity, pain, anxiety, depression and improved cognition. The intervention may also reduce potential harms from short-term, and possibly long- term use of opioids and benzodiazepines, recognized as potentially inappropriate medications according to the American Geriatrics Society Beer's Criteria. Discontinuation of medications with adverse cognitive effects may improve short- and long-term cognitive performance. The improvement in cognitive function may or may not be noticeable to study participants. This research could also provide a non-pharmacological approach for delirium management in ICU patients.

The intervention proposed in this study builds upon prior research and may hold promise for an effective and scalable recovery model for this population. This intervention does require additional resources that will cost additional money; however, it is possible that these short-term costs will be offset by reductions in overall costs to patients and the healthcare system. While risks associated with this proposed study are thought to be low, findings have the potential to be applied to the million patients who receive mechanical ventilatory support each year in the United States. If the findings from this investigation support the research hypothesis, mechanically ventilated patients who listen to music would experience fewer of the side effects documented to occur with these symptom management regimens that rely solely on potent sedative medications. This in turn may lead to patients being weaned quicker from mechanical ventilation, which would decrease the suffering and burdensome symptoms associated with mechanical ventilation such as fewer ventilator-associated pneumonias which could lead to reduced complications and costs for ICU medical care.

4. Importance of Knowledge Gained: Up to 80% of ICU patients develop delirium and currently there are no effective and scalable treatment modalities. Our proposed intervention may provide a conceptual and scalable recovery model to remediate or treat ICU delirium and its deleterious effects on cognition.

4. DATA AND SAFETY MONITORING PLAN

The MPIs ([name], [name]) and a safety officer will monitor the study.

- **1.** Qualifications and responsibilities of the Safety Officer: The safety officer for this trial will be a clinical researcher experienced in running intervention studies. The safety officer will review the reports sent by the study manager to determine whether there is any corrective action, trigger of an ad hoc review, or stopping rule violation that should be communicated to the study primary investigator, the Indiana University IRB, and the NIH. In addition, the safety officer may comment on whether the study investigators need to report any specific out of range data to the participant and/or her physician. As with our prior trials, the safety officer will receive a monthly report of all events that occurred during the month.
- **2. Monitoring and Reporting:** The frequency of data reviews for this study differs according to the type of data and can be summarized in the following table:

Data Type	Frequency of Review		
	Each Occurrence	Q 6 months	Annual
Subject accrual (adherence to		X	
inclusion/exclusion); drop-out			
rates; randomization			
Adverse event rates	X	X	
Subjects' Complaints		X	
Compliance to Interventions		X	
Protocol Violation/Non-compliance	X	X	
Risk Benefit Ratio Assessment			Х
Stopping Rules Report			X

The study coordinator and biostatistician will generate reports for PI, and safety officer that will contain:

- Summary of adverse events and an explanation of how each event was handled,
- Summary of complaints and how each complaint was handled,
- Subject retention, including the number and reasons of participant withdrawals,
- Intervention compliance (session attendance), and
- Summary of protocol violations and how each was handled. All reports will be submitted to IU IRB at time of continuing review.
- 3. Measurement and reporting of adverse events: Adverse event rates associated with music intervention are low. Therefore, adverse event rates are expected to vary little between the treatment and control groups. We will present blinded adverse event data to the statistician and PI throughout the trial. We plan to present unblinded adverse events data to the safety officer throughout this trial and as requested by the safety officer and at annual meetings. If there is evidence of elevated adverse events, the safety officer will consult with the statistician and PI. The study staff will use an adverse event form to report adverse events caused by the intervention.

4. Possible Adverse Events: Adverse events will be monitored on an ongoing basis by the study coordinator. The PI will be notified within 24 hours of any adverse events. Serious adverse events will be reported within 5 business days to IU IRB, Safety Officer, and NIH. Non-serious adverse events will be reported weekly to the safety officer and at time of continuing review to IU IRB. In cases where there is any question regarding the level of adverse events or attributable cause, we will consult with the safety officer.

The information collected will include the following:

- Description of the AE.
- Time and Date of onset and eventual date of resolution or death, if available.
- Frequency: intermittent, single occurrence, or continuous.
- Severity of the event.
- Action taken, including use of any concomitant treatment or medication.
- Outcome.
- Relationship to study treatment regimen or other causality.
- **5. Stopping Rules:** It is unlikely that the study would be stopped early due to important favorable differences in the intervention group compared to control group because of the short-term nature of the intervention. However, the study could be stopped early due to adverse events. The NIA will make the final decision on whether or not to accept the safety officer's recommendation about discontinuation of any component of the study.
- **6. Limits of Assumptions:** It is possible that baseline differences between the groups, excessive study dropouts and/or missing data by the interim measurement time point (midway point to targeted enrollment) will limit the value of data analysis. Baseline differences will be evaluated after the first measurement time point and effects on the power to detect differences in the primary outcome will be evaluated and communicated to the PI, safety officer, and NIA. Given the monitoring plans outlined elsewhere in this document, it is exceedingly unlikely that there will be baseline differences between groups of any magnitude to threaten the validity of the study.

Dropout rates higher than 15% would be of concern, so we propose to monitor the dropout rate quarterly. Alert points are set at dropout rates of 15% (low alert), 25% (mid-alert), 35% (high alert) and 45% (extreme alert).

With early alerts to problems, action would be taken to avoid higher-level alerts; if a higher-level alert should arise, more drastic remedial action would be invoked.

The actions taken at each level of alert are given below:

- Mid-level alert = Conference call between study investigators to discuss approaches to minimize further losses to follow-up/dropouts.
- High-level alert = Conference call between investigators and safety officer to determine further alterations of study protocol to complete the study with no further losses.
- Extreme-level alert = In the unlikely event of a 45% dropout rate occurs prior to the six-month measurement time point, study investigators, the safety officer, and the NIA program official would convene on a conference call to discuss the usefulness of continuing the study.

Additional Protocol Materials based on Supplemental Funding

Changes added with protocol amendment 5/22/2023

- 1. Add baseline(prior to/around hospital discharge) and longitudinal outcomes assessment (month 6, month 12) data collection timepoints
 - A. Cognition: Cognition will be measured by 4 objective tests of memory, attention, information processing speed, and executive cognitive function (Auditory Verbal Learning Test [AVLT], Digit Span, and Symbol Digit Modalities Test [SDMT], and Controlled Oral Word Association test [COWA]) using a telephone-based administration format, the Indiana University Telephone-Based Assessment of Neuropsychological Status (IU-TBANS) prior to/around hospital discharge, at 3-months post hospital discharge, 6 months post-hospital discharge.

Previous research has demonstrated that these tests can be delivered reliably and precisely **in** person or by telephone.⁸⁴

- B. Depression and Anxiety: Research staff will collect PHQ-9 and GAD-7 over the phone or in person prior to/around hospital discharge, at 3 months post-hospital discharge, 6 months post-hospital discharge and 12 months post-hospital discharge.
- 2. Add Blood Sample Collection Time points (month 3, month 6, month 12).

During hospitalization we will collect blood samples prior to first intervention session (up to 10ml in tubes containing anticoagulant), at day 3, and at the end of the intervention period (up to 10 ml in tubes containing anticoagulant). Samples will also be collected at the month 3, month 6 and month 12 post hospital discharge visits (up to 10ml in tubes containing anticoagulant) in the clinic. This will be a total of up to 4 tablespoons of blood collected. The samples will be transported to the CTSI lab, and will be prepared and stored using deidentified labels.

3. Exploratory Aims added (1,2):

Exploratory Aim 1: Test the efficacy of the DDM treatment in slowing the rate of post-ICU cognitive decline in mechanically ventilated patients as compared to attention control. Hypothesis 1a: Patients in the DDM intervention group will have slower cognitive decline compared to the attention control group as measured by the IU-TBANS completed at 6- and 12-months after hospital discharge. Hypothesis 1b: This difference in cognitive trajectories between the DDM intervention group versus the attention control group will be due, in part, to the DDM treatment decreasing the duration and severity of ICU delirium during the index ICU stay.

[figure not shown]
Exploratory Aim 2: Determine whether the DDM treatment is associated with slower progression of ADRD pathology in older adult ICU survivors as compared to attention control. Hypothesis 2a: Patients in the DDM treatment group will have slower progression in measures of neurodegeneration (lower level of neurofilament light (NfL), phosphorylated tau-181 (p-tau 181), glial fibrillary acidic protein (GFAP), and S100B), AD pathology (higher levels of Aβ42/Aβ40), vascular pathology (lower levels of C-reactive protein (CRP))⁸ and inflammation (lower levels of interleukins (IL)-1, 6, and 8) as measured by blood-based biomarkers collected in the ICU and 3, 6 and 12 months after hospital discharge, compared to those in the attention control group. Hypothesis 2b: These differences in progression of ADRD pathology between the DDM treatment versus control group will be due, in part, to the DDM treatment decreasing the duration and severity of ICU delirium during the index ICU stay.

4. Exploratory Aims Statistical Considerations added (1,2)

Exploratory Aim 1: Mixed effects models will be used with repeated IUTBANS scores (collected at baseline, 6 months and 12 months as the outcome measures), group, time, and a group and time interaction as independent variables while adjusting for stratification variables and other potential baseline covariates found to be significantly different in univariate comparisons. A significant interaction between group and time would indicate differences in changes of cognitive functions over time between the two groups.

Exploratory Aim 2: Changes in the biomarkers will be calculated and used as the dependent variables in ANCOVA models with group as the independent variable and adjusting for stratification variables and baseline covariates that are found to be different among the groups in univariate comparisons. Mixed effects models will be used to explore the association between oxidative stress biomarkers at ICU admission and those collected at 3, 6-, and 12- months post discharge.

5. Revised Figure 3: DDM Trial Flow Chart

6. Revised Table Time-line of Data Collection and Outcomes Assessments

			ata Collection a					
Co	Method of Collection	ne-line of Data Collection and Outcome ICU Phase			Hospital Discharge	Post Hospital Discharge		
		Enrollment	Intervention Phase	Post- intervention phase		3 months	6 months	12 months
Demographics (Age, race, gender, education, Insurance)	EMR	Х						
Clinical Data (lab	EMR	Х						
Comorbidities (Charlson) ^a	EMR	Х						
Baseline Cognitive function (IQCODE) ^b	Caregiver Interview	Х						
History of depression, Anxiety	EMR	Х						
Diagnoses	EMR	Х			Х			
Severity of Illness ^c (APACHE II, SOFA)	EMR	X (APACHE)						
Functional Status ^d (ADL, IADL)	EMR	Х						
Medications	EMR, patient, caregiver	Х	Daily	Daily	Х	Х	Х	Х
Duration of Mechanical Ventilation, Length of ICU and Hospital stay	EMR				Х			
Mortality	EMR				Х			
Discharge Disposition	EMR				X			
ABCDEF bundle adherence	EMR, Nursing reports	Х	Daily	Daily				
Intervention characteristics	iPad App and Web portal	Х	Х					
Physiologic Parameters (respiratory rate, heart rate, blood pressure)	EMR	Х	4X Daily	Daily				
Delirium, Pain, Anxiety ^f (RASS, CAM- ICU, CAM-ICU-7, CPOT, VAS-A)	Direct Assessment		2X Daily (CAM-ICU, CAM-ICU-7), 4X Daily (RASS, CPOT, VAS-A)	2X Daily				
Cognition (IUTBANS)g	Direct Assessment		, ,		Х	Х	Х	Х
Mood Symptoms ^h (GAD-7, PHQ-9)	Direct Assessment				Х	Х	Х	Х
ICU Experience, Music preference ^{j and}	Direct Assessment				Х			
Specimen collection	Direct Assessment	Х	Х	х		Х	Х	Х
Healthcare Utilization ⁱ	EMR, INPC							Х

°Chronic comorbidities measure through Charlson Comorbidity Index⁸⁹, bIQCODE: Informant Questionnaire on Cognitive Decline in Elderly⁹⁰, Severity of Illness measured through APACHE II⁹¹ and SOFA⁹², Functional Status measured through Katz and Lawton Scales^{93,94}, Analgesic and sedative exposure is defined as aggregate measure of pain and sedation intensity and the drug frequency in a 24 hour period. We will aggregate dose frequency and dosing intensity by each enrollment day. A dose frequency analysis will be used ⁹⁵⁻⁹⁷. FRASS: Richmond-Agitation Sedation Scale⁷⁶, CAM-ICU: Confusion Assessment Method in the ICU⁷⁵, CPOT: Critical Care Pain Observation Tool⁷⁸, VAS-A: Visual Analog Scale-Anxiety⁸¹, gIUTBANS: Indiana University Telephone-Based Assessment of Neuropsychological Status⁸⁴, PHQ-9: Patient Health Questionnaire⁸⁵, GAD-7: Generalized Anxiety Disorder Scale⁸⁷, Captured through Indiana Network for Patient Care (INPC), Intensive Care Experience Questionnaire, Music Preferences Questionnaire. kWe will obtain the Richard-Campbell Sleep Questionnaire around time of extubation (once patient can communicate), at hospital discharge, and at 3-, 6-, and 12-months.

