2. REPORTING OF ADVERSE EVENTS

Safety: Patients will be monitored for adverse events on a daily basis. Adverse events will be reported to the Institutional Review Board (IRB), data safety officer and contact MPI [name] immediately. In our prior work, we have not experienced any adverse events related to the study protocols. All infection control guidelines will be followed based on each hospital's policy. Patient risks will be minimized through use of quality electronic devices, regular cleaning and maintenance. Lastly, given the high-intensity nature of the ICU, all patients will receive benefit from frequent monitoring in the ICU as part of routine care.

Study Withdrawal/Discontinuation: Participants who wish to withdraw from the study will notify the study team verbally during study interactions or via letter as outlined in the HIPAA authorization document.

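### The adverse event form is tied to events attributed to the intervention, in conflict with the wider capture described elsewhere; separately, reporting times to the IRB and safety officer differ between sections

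*Combined protocol and SAP*

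**What the plan says.** **Scope of recording.** Under Measurement and reporting of adverse events (item 3 of the Data and Safety Monitoring Plan), the purpose of the form is given as: "The study staff will use an adverse event form to report adverse events caused by the intervention". Item 4 of that plan, Possible Adverse Events, lists the information to be collected, including: "Relationship to study treatment regimen or other causality". Item 1 says that "the safety officer will receive a monthly report of all events that occurred during the month". The section Reporting of Adverse Events states: "Patients will be monitored for adverse events on a daily basis"; Protections Against Risk (2.b, item 3) says the same.

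**Reporting times.** Reporting of Adverse Events says "Adverse events will be reported to the Institutional Review Board (IRB), data safety officer" and a principal investigator, and the sentence ends by requiring this immediately. Protections Against Risk repeats it: "Adverse events will be reported to the Institutional Review Board (IRB), data safety officer, and PIs immediately". Item 4 of the monitoring plan says instead: "Serious adverse events will be reported within 5 business days to IU IRB, Safety Officer, and NIH". It sends non-serious events to the safety officer weekly and to the IRB at continuing review, and gives 24 hours for telling the PI of any event.

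**Who sees what.** Section 6 (Blinding) keeps everyone blinded except the patient and the staff member who assigns the intervention. Outcomes Assessments, in the same section, adds that this staff member also delivers it. The monitoring plan has the study coordinator monitor events, unspecified study staff use the form, and the safety officer receive unblinded data.

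**The concern.** A form reserved for events attributed to the intervention puts the causality judgement before the record. An event judged unrelated never reaches the form, so its relationship field is never filled in and nobody can revisit the judgement. The phrase is also hard to apply evenly. The protocol names an adverse emotional response to a piece of music as a risk, and a silence track has no obvious counterpart.

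At stake is the safety officer's review. It is the only place where adverse events are to be seen by arm, and the Stopping Rules item says the study could stop early because of adverse events. If readiness to attribute an event differs between arms, that review could show a difference that is not there or miss one that is.

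The reporting times are a separate matter of conduct: a site that meets the monitoring plan's deadlines could be in breach of the other two sections.

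**Working it through.** The documents give no adverse event rate and no figure for how often events are attributed to treatment. There is nothing to recompute, so the check is a comparison of the texts.

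**1. Scope of recording**

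| Place | What is covered | Limited by cause? |
|---|---|---|
| Monitoring plan, item 3 (form sentence) | Events put on the form | Yes |
| Monitoring plan, item 4 (information list) | Relationship to treatment or other cause | No; presupposes events of other cause |
| Monitoring plan, item 4 (notification) | Any event to the PI; serious events to IRB, safety officer and NIH | No |
| Monitoring plan, item 1 | Monthly report of all events | No |
| Reporting of Adverse Events; Protections Against Risk | Daily monitoring | No |

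One sentence limits scope by cause and the others do not. The limiting sentence is also the only one that says what the form is for, and no other adverse event recording instrument is named. Staff following it literally would leave out an event they judged unrelated. Staff following the monthly-report sentence would include it. Sites could differ.

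**2. What a literal reading does to counts by arm.** Let r be the true event rate in an arm and a the chance that an event is judged to be caused by the intervention. The recorded rate is r × a.

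- If r is the same in both arms, the ratio of recorded rates is a(music) / a(control). It equals 1 only if attribution is equally likely in both arms.
- If a is the same in both arms but below 1, the ratio is preserved, but both counts shrink and a real difference is harder to see.

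No values for a are available, so only the direction of the problem can be stated.

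**3. Who judges cause.** The coordinator monitors and study staff use the form. One staff role is unblinded and is present when sessions are delivered. No sentence says that this person may not complete the form, or that whoever judges relationship is blinded.

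**4. Reporting times**

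| Event class | Recipient | Reporting of Adverse Events; Protections Against Risk | Monitoring plan, item 4 |
|---|---|---|---|
| Serious | IRB | Immediately | Within 5 business days |
| Serious | Safety officer | Immediately | Within 5 business days |
| Non-serious | Safety officer | Immediately | Weekly |
| Non-serious | IRB | Immediately | At continuing review |
| Any | PI | Immediately | Within 24 hours |

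The four IRB and safety officer rows do not agree. The PI row can be read as one rule. The monthly report to the safety officer may be a cumulative summary, so it is weak evidence of a further conflict.

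**The case against.** The strongest reply is that the documents as a whole point to broad capture. A reader might infer that only events caused by the intervention are recorded, but the word only is not there. The relationship item, the report of all events and the unrestricted daily monitoring all point the other way. That stands. The defect is a conflict between sentences, not a settled rule of exclusion.

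A reader might also infer that unblinded staff filter the events. The documents do not say so. All roles but one are blinded apart from the patient, the coordinator does the monitoring, and doubtful questions of cause go to the safety officer. What remains is that the blinding of the person judging cause is not specified, and that consultation helps only with events someone has already raised.

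Nor is there a planned comparison of harms to be biased. Statistical Considerations contains none, and the NIA makes the final decision on any recommendation to discontinue. The exposure is confined to the safety officer's review and any later reporting that uses the same data.

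Some information bypasses the form. The app logs session length in both arms. Safety reports cover complaints, withdrawals with reasons and session attendance. Mortality is collected separately. This limits what could be lost, but it does not settle what the form should hold.

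On reporting times, it would be wrong to say staff cannot comply: immediate reporting also meets a 5-day limit, and later reports can be summaries. The times remain unreconciled, because a site relying on the longer limits would not meet the shorter one. The timing conflict does not cause the scope problem; the two are independent.

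**Conclusion.** Two separate inconsistencies stand, both of low priority.

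First, the form sentence conflicts with the relationship item, the daily monitoring and the report of all events. Read literally, it screens events on cause before they are recorded. The possible effect on the safety officer's view by arm depends on two conditions that the documents leave open: that staff follow the sentence as written, and that readiness to attribute differs between arms. Its size cannot be derived, and no rate is assumed here.

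Second, reporting times to the IRB and the safety officer disagree for both serious and non-serious events. This needs no assumption; it is visible from the text. The primary and secondary efficacy analyses are not affected by either point.

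**What to change.** - Reword the form sentence so that, in both arms, all serious events and a short listed set are recorded regardless of cause. The set would be headphone skin injury or discomfort, emotional distress, and a session stopped early.
- State that relationship to the intervention is judged after recording, by a named existing role that is blinded to arm.
- Reconcile Reporting of Adverse Events, Protections Against Risk, and items 1 and 4 of the Data and Safety Monitoring Plan, so that each event class has one reporting time per recipient. Say whether the monthly report is a summary. Which times to adopt is for the sponsor and the IRB.

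The cost is a few more short forms and a text edit. The listed set avoids having to record every ICU event, and no new blinded role is needed.
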